# 6.5.9 Additional Sensitivity Analyses of Primary and Key Secondary Outcomes

Sensitivity analyses of primary and key secondary efficacy outcomes are the same as specified in the M-SAP.

# **6.5.10 Subgroup Analyses**

In addition to the subgroups specified in the M-SAP, the following additional subgroups will be analyzed in the random-slope model (see Section 6.5.3) for primary and secondary efficacy endpoints in the FAS analysis set:

- Baseline use of riluzole and edaravone (neither, riluzole only, edaravone only, both),
- Age (less than 65 years vs. 65 years or older),
- Sex (female vs. male),
- Race (white vs. any minority race with greater than 5% prevalence in the sample),
- Ethnicity (Hispanic or Latino vs. non-Hispanic or Latino),
- Weight (less than 70 kg, 70 to less than 85 kg, 85 kg or more),
- BMI (less than  $18.5 \text{ kg/m}^2$ ,  $18.5 \text{ to less than } 25 \text{ kg/m}^2$ ,  $25 \text{ kg/m}^2$  or more),
- Chronic kidney disease (CKD) stage (stage 1 or better [eGFR 90 mL/min/1.73m^2 or more], stage 2 [eGFR 60 to 89 mL/min/1.73m^2], stage 3 or worse [eGFR less than 60 mL/min/1.73m^2]),
- Time since onset of weakness (less than 18 months vs. 18 months or longer),
- Baseline serum NfL concentration (by median split), and
- Site (individual sites with at least 5 participants per treatment group and all participants from sites with fewer than 5 participants per treatment group pooled).

For each classification, unknown, not reported, and missing will be considered one group. All individuals not included in a specified subgroup will be combined into a mixed, "other" group. The "other" group will be included in analyses if its prevalence is greater than 5%; otherwise, the "other" group will be excluded.

In cases where a model for a given subgroup and endpoint fails to converge, the covariance terms for the regimen-specific random effects will be simplified from unstructured covariance of intercepts and slopes to separate, uncorrelated variance components for intercepts and slopes. If convergence still fails, regimen-specific intercepts and slopes will be modeled as fixed effects. If convergence still fails, the participant-specific random effects will be simplified from unstructured covariance of intercepts and slopes to separate, uncorrelated variance components for intercepts and slopes.

# 6.5.11 Comparison of Controls across Regimens

Comparisons of placebo participants across regimens are the same as specified in the M-SAP with separate analyses that include baseline serum NfL level as an additional covariate in adjusted analyses plus applicable interaction terms as relevant to a given model.

#### **6.5.12 Pharmacokinetic Analyses**

Pre-dose concentrations of verdiperstat in plasma will be summarized by treatment group and visit in the ERO sample. Concentrations below the limit of quantitation (BLQ) will be replaced with one half of the lower limit of quantitation. Summaries will include number of observations, number and percentage with concentrations BLQ, arithmetic mean, median, standard deviation, minimum, maximum, geometric mean, geometric coefficient of variation (calculated as sqrt(exp(variance of log-transformed concentrations) – 1)), and 95% confidence bounds for the geometric mean assuming log-normally distributed data.

Plasma concentration data of verdiperstat may be subjected to population pharmacokinetic analysis to derive population estimates of pharmacokinetic parameters and test the effect of various covariates such as age, weight, and sex. Details of the analysis will be described in a separate data analysis plan (DAP). This analysis may be performed by combining data from the current study with data from other studies of verdiperstat, if deemed appropriate. The population pharmacokinetic analysis will be performed by Biohaven and reported in a separate modelling report.

# 6.5.13 Pharmacodynamic Biomarker Analyses

Change in myeloperoxidase protein and activity levels in plasma will be summarized by treatment group and visit in the ERO sample. Summary statistics will be provided for the values, change from baseline, and percent change from baseline at each scheduled assessment time point. Myeloperoxidase protein and activity levels in plasma will be analyzed in a repeated-measures linear mixed model that includes fixed terms for visit, time from last dose of verdiperstat, and time from last meal.

# 6.6 Safety Analyses

#### **6.6.1** Treatment-emergent Adverse Events

Summaries and analyses of treatment-emergent adverse events (TEAE) are the same as specified in the M-SAP with the following revisions.

TEAEs are defined as those adverse events with onset dates in the interval from double-blind treatment initiation to the earliest of the Final Safety Visit, the date the participant dies, early terminates, or is lost to follow-up, 28 days after last dose of study drug, or the date of first dose of study drug during participation in the OLE, if so exposed. Adverse events with onset on the day of double-blind treatment initiation and adverse events with incompletely specified onset date where the ambiguous date spans the day of double-blind treatment initiation or the earliest of the events above that define the end of the treatment-emergence interval will be assumed to be treatment emergent except for those known to precede first exposure to study drug.

In addition to summaries specified in the M-SAP, the following categories of adverse events will be summarized by Medical Dictionary for Regulatory Activities (MedDRA) system organ class and preferred term: (a) all adverse events, including those not classified as TEAEs, (b) fatal TEAEs, and (c) TEAEs that occurred during a participant's COVID-19 infection (defined as 5 days prior to symptom onset to end of COVID-19 symptoms or end of double-blind follow-up, if ongoing).

TEAEs indicating COVID-19 infection are the following: Asymptomatic COVID-19, COVID-19, COVID-19 pneumonia, COVID-19 treatment, Post-acute COVID-19 syndrome, SARS-CoV-

2 antibody test positive, SARS-CoV-2 RNA increased, SARS-CoV-2 sepsis, SARS-CoV-2 test false negative, SARS-CoV-2 test positive, SARS-CoV-2 viraemia, Suspected COVID-19.

Treatment-dependent differences in the proportion of participants experiencing a given type of TEAE will not be tested. Treatment-dependent differences in TEAE incidence rates in units of number per 100 participant years will be estimated as differences rather than ratios, will include comparison-wise 95% confidence intervals with variance estimates obtained by the delta method, and will be provided for overall classes of TEAEs not further classified by MedDRA term (all TEAEs, serious TEAEs, severe TEAEs, TEAEs leading to discontinuation of study drug, TEAEs resulting in death, and TEAEs of special interest) and TEAEs with at least 5% prevalence in the active arm.

Listings will document all adverse events (including those not classified as treatment emergent), TEAEs, serious TEAEs, severe TEAEs, related TEAEs, TEAEs leading to discontinuation of study drug, TEAEs resulting in death, and TEAEs of special interest.

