| Install Smartphone App ²¹ | Regimen | | | X | | | | | | | | |
| Voice Recording ¹² | Regimen | | | X | | X | X | | X | | X | |
| Uninstall Smartphone App | Master | | | | | | | | | | X | |
| Assignment to the Regimen | Master | X | | | | | | | | | | |
| Randomization within the Regimen | Master | | | X | | | | | | | | |
| Administer/Dispense Investigational product | Regimen | | | X ¹³ | | X | X | | X | | X ¹⁴ | |

| Activity | Master Protocol or Regimen-Specific | Master Protocol Screening ¹ | Regimen Specific Screening ¹ | Baseline | Week 2 ² | Week 4 ^{18,19} | Week 8 ^{18,19} | Week 12 | Week 16 ^{18,19} | Week 20 | Week 24 or Early Term. Visit ^{3, 18} | Follow-up Safety Call ^{3,4} |
|--------------------------------------|-------------------------------------|--|---|-----------------|---------------------|-------------------------|-------------------------|-----------------|--------------------------|-----------------|---|--------------------------------------|
| | | Clinic | Clinic | Clinic | Phone | Clinic | Clinic | Phone | Clinic | Phone | Clinic | Phone |
| | | -42 to -1 Days | -41 to 0 Days | Day 0 | Day 14 \pm 3 | Day 28 \pm 7 | Day 56 \pm 7 | Day 84 \pm 3 | Day 112 \pm 7 | Day 140 \pm 3 | Day 168 \pm 7 | 28 \pm 7 days after last dose |
| Study Drug Accountability/Compliance | Master | | | | X ^{2,22} | X | X | X ²² | X | X ²² | X | |
| Dose Escalation | Regimen | | | X ¹⁵ | X ¹⁵ | | | | | | | |
| Exit Questionnaire | Master | | | | | | | | | | X | |
| Vital Status Determination | Master | | | | | | | | | | X ¹⁶ | |

¹ Master Protocol Screening procedures must be completed within 42 days to 1 day prior to the Baseline Visit. The Regimen-Specific Screening Visit and Baseline Visit should be combined if possible.

² At the end of Week 2, an assessment of compliance and tolerance to this dose titration schedule will be conducted. The assessment will be conducted by phone. If tolerability issues are experienced with 300 mg QD or 300 mg BID dosing, the titration schedule may be modified (see Section 5.3.2).

³ Participants will only have a Follow-Up Safety Call at this time if they *do not* continue into the OLE or if they discontinue prior to Week 24. Participants who continue into OLE will have a Follow-Up Safety Call after their last dose of study drug during the OLE phase.

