5.3.2 Dosage Modification

Participants will be instructed on the dosing regimen. If tolerability issues are experienced during the dosage titration period with the 300 mg QD and/or 300 mg BID doses (or matching placebo), the titration schedule may be extended (e.g., up titration to the next dosage level delayed by an additional week). Potential tolerability issues may include sudden, clinically significant changes from baseline in symptoms of presyncope, syncope, orthostatic hypotension, or falls that are not otherwise explained. The SI must consult with the Medical Monitor if he or she believes that a change to the dosage titration schedule is warranted; and, the SI must document any such changes to the dosage titration schedule.

During the full dose period of the study, it is anticipated that all participants will receive either verdiperstat 600 mg BID or matching placebo BID. If participants have difficulty tolerating verdiperstat 600 mg BID or matching placebo BID dosing, the SI may permit the participants to switch to verdiperstat 300 mg BID or matching placebo BID dosing (and document this change in the participant's records). Potential tolerability issues may include those listed above as well as clinically significant laboratory abnormalities (i.e., thyroid and renal function) that are not otherwise explained. Down titration to verdiperstat 300 mg BID or matching placebo BID will only be allowed to address tolerability issues and only with Medical Monitor approval. If a participant is down titrated to the 300 mg BID dose, they may be allowed to retry the 600 mg BID dose (re-challenge), if deemed appropriate by the SI and Medical Monitor. Only two re-challenges are allowed. Any such changes must be documented. If a switch to verdiperstat 300 mg BID or matching placebo BID dosing does not result in acceptable tolerability, then dosing should be discontinued.

Dosage modification should be considered if a participant experiences one of the following:

- a. Clinically significant changes in frequency and/or severity from baseline in symptoms of presyncope, syncope, orthostatic hypotension, and/or falls that are not explained by disease progression or intercurrent illness and not able to be adequately treated with symptomatic pharmacological and non-pharmacological treatments, based on the judgement of the SI.

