# 1. Governing Documents

This Regimen-specific Statistical Analysis Plan (R-SAP) for the verdiperstat regimen (RGB) specifies any modification from the default outcome measures, analysis samples, and planned analyses for the placebo-controlled period of the HEALEY ALS Platform Trial as specified in the Master SAP (M-SAP). The M-SAP and this R-SAP supplement the Master Protocol, the "ALS Master Protocol Recommended Statistical Analysis, Design and Simulation Report" (Appendix 1 to the Master Protocol), and the RGB Regimen-specific Appendix (RSA). Please refer to the Master Protocol and the RGB RSA for details on the rationale for the study design, eligibility criteria, conduct of the trial, clinical assessments and schedule of assessments, definitions and reporting of adverse events, data management conventions, and regulatory oversight and compliance procedures. The "ALS Master Protocol Recommended Statistical Analysis, Design and Simulation Report" (MPRDR) and any regimen-specific deviations described in the RGB RSA and this R-SAP are authoritative in defining the primary and interim analyses. In case of discrepancies between the RGB RSA and this R-SAP concerning use of shared placebos, this R-SAP is authoritative. In case of discrepancies between either SAP and the Master Protocol and the RGB RSA concerning matters of analysis other than the primary and interim analyses and use of shared placebos, the M-SAP and this R-SAP are authoritative. In case of discrepancies between the M-SAP and this R-SAP, this R-SAP is authoritative. On all matters not related to analysis, the Master Protocol and the RGB RSA are authoritative. The following table describes relationships among the relevant documents in adjudicating possible discrepancies with higher numbers indicating greater authority.

Issues potentially requiring adjudication	Master Protocol	RGB RSA	MPRDR	M-SAP	RGB R-SAP
Use of shared placebos	1	4	2	3	5
Primary and interim analysis specifications not related to use of shared placebo	1	5	4	2	3
Statistical analysis specifications not related to use of shared placebo or primary and interim analyses	1	3	2	4	5
All matters not related to statistical analysis	4	5	1	2	3

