<sup>8 Clinical safety labs include hematology (CBC with differential), complete chemistry panel, thyroid function (TSH) and urinalysis. Serum pregnancy testing will occur in women of child-bearing potential at the Master Protocol Screening Visit and as necessary during the study. Pregnancy testing is only repeated as applicable if there is a concern for pregnancy.

<sup>9 Adverse events that occur after signing the master protocol consent form will be recorded.

<sup>10 Myeloperoxidase protein and activity, and plasma concentrations of verdiperstat will be measured. For each sample, the time of the last verdiperstat or matching placebo dose prior to sample collection, time of the last meal prior to sampling and time of the PD/PK sample collection should be reported on the CRF.

<sup>11 The DNA sample can be collected after baseline if a baseline sample is not obtained or the sample is not usable.

<sup>12 In addition to study visits outlined in the SOA, participants may be asked to complete twice weekly voice recordings at home. During weeks when a participant is doing a voice recording in-clinic, he or she would only do one other voice recording at home that week.

-  Vital status, defined as a determination of date of death or death equivalent or date last known alive, will be determined for each randomized participant at the end of the placebo-controlled portion of their follow-up (generally the Week 24 Visit, as indicated). If at that time the participant is alive, his or her vital status should be determined again at the time of the last participant's last visit of the placebo-controlled portion of a given regimen. We may also ascertain vital status at later time points by using publicly available data sources as described in section 8.15 of the Master Protocol.
-  If the CSF collection cannot happen at the Week 16 Visit for logistical reasons such as scheduling, it can happen at the Week 24 Visit.
-  Participants should be instructed to skip the morning dose of study drug on the day of the study visit. Study drug should not be taken until after study visit procedures are complete.
-  Visit may be conducted via phone or telemedicine with remote services instead of in-person if this is needed to protect the safety of the participant due to a pandemic or other reason.

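### SAP 6.6.1 defines TEAEs by onset date alone, so a pre-dose adverse event that worsens or becomes serious on treatment can drop out of the TEAE counts and rate differences

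*SAP*

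**What the plan says.** SAP 6.6.1 opens with "Summaries and analyses of treatment-emergent adverse events (TEAE) are the same as specified in the M-SAP with the following revisions" and then gives its own definition: "TEAEs are defined as those adverse events with onset dates in the interval from double-blind treatment initiation". The interval ends at the earliest of the final safety visit, death, early termination, loss to follow-up, 28 days after last dose, or first open-label dose.

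Events that start on the day of first dose, and events whose incomplete onset date spans that day or the end of the interval, "will be assumed to be treatment emergent except for those known to precede first exposure to study drug".

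On which document governs, SAP section 1 says: "In case of discrepancies between the M-SAP and this R-SAP, this R-SAP is authoritative". The same section sends the reader to the Master Protocol and the regimen appendix for "definitions and reporting of adverse events".

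On timing, footnote 9 of the Schedule of Activities in SAP 2.9 says "Adverse events that occur after signing the master protocol consent form will be recorded", and footnote 1 of the protocol's schedule says "Master Protocol Screening procedures must be completed within 42 days to 1 day prior to the Baseline Visit".

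SAP 6.6.1 estimates between-arm differences in events per 100 participant-years, with 95% confidence intervals. It does so for all TEAEs; for the serious, severe, discontinuation, fatal and special-interest classes; and for TEAEs with at least 5% prevalence in the active arm. Differences in the proportion of participants with a TEAE are not tested.

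**The concern.** A TEAE definition usually has two parts: events that begin on treatment, and events present before treatment that get worse on it. SAP 6.6.1 has only the first.

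Treatment-emergent adverse and serious adverse events are the first safety endpoint listed in protocol section 2, and the only AE comparisons with confidence intervals in SAP 6.6.1 are built on TEAEs. If the drug aggravates symptoms that some participants already have on record, that part of its effect is missing from the estimated rate difference. The severe and serious classes are the most exposed, because a mild screening event that becomes severe or serious on treatment is what a worsening clause is meant to catch.

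The plan measures change from baseline elsewhere. SAP 6.6.2 uses shift tables against baseline for laboratory toxicity and for hypothyroidism. Protocol 5.3.2 lists "Clinically significant changes in frequency and/or severity from baseline in symptoms of presyncope, syncope, orthostatic hypotension, and/or falls" among the triggers for considering a dosage change. The supplied text has no comparable device for clinical AEs in general.

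**Working it through.** No arithmetic applies. The check is whether the events can exist, how the rule classifies them, and what else would show them.

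**Can such records exist?** Yes. AE recording starts at Master Protocol consent, screening may start 42 days before Baseline, and the first dose is given at the Baseline Visit after all assessments. Any AE that begins between consent and that dose has a pre-dose onset date.

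**How does the rule classify them?**

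| Case | Onset | Course | Recorded as | TEAE under 6.6.1? |
|---|---|---|---|---|
| 1 | Day -20, mild | Severe or serious on Day 30 | One record | No |
| 2 | Day -20, mild | Severe or serious on Day 30 | New AE, onset Day 30 | Yes |
| 3 | Day of first dose | Any | One record | Yes, unless known to precede the dose |
| 4 | Partial date spanning first dose | Any | One record | Yes, unless known to precede the dose |
| 5 | Day 30, mild | Severe later | One record | Yes |

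Case 1 is the gap. The event is absent from the all, serious and severe TEAE counts. If it leads to stopping study drug or to death, it is also absent from those classes. Case 2 shows that the gap closes if worsening is re-recorded. Case 4 shows that some events that truly began in screening are counted because their date is imprecise.

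**Could another supplied provision fill the gap?** None was found. The protocol does not define treatment-emergent. The master SAP (M-SAP) was not available. If it has a worsening clause, that clause would not clearly survive, because 6.6.1 presents its definition as a revision and the regimen SAP prevails.

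**Where do case 1 events still appear?**

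- All-AE summary by system organ class and preferred term, and all-AE listings (6.6.1): yes, but without a rate difference.
- Time to first hospitalization for an SAE (5.11, 6.5.4): measured from Baseline with no TEAE condition in its definition, so a worsening that leads to a non-elective hospitalization can count.
- Survival and death alone (5.9, 6.5.4): deaths count whatever the AE onset date.
- Laboratory and thyroid shift tables (6.6.2): these capture worsening from baseline in those domains.
- Study drug interruption and dosage reduction (6.7.2): these capture the dosing consequence, not the event.

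**How many events?** A count would need the rate of AEs arising between consent and first dose, the share still ongoing at first dose, the share that then worsen, and the share kept as one record. The documents give none of these.

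**The case against.** The strongest objection is that the deciding fact lies outside the file. A rule keyed to onset dates depends on how sites create records, and SAP section 1 refers AE definitions and reporting to the Master Protocol. If that document requires a new AE entry for each worsening or change to serious, the rule works as written. This stands, and it is why the point is conditional. It does not remove the point, because 6.6.1 neither states nor cites such a convention.

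Several stronger readings are tempting but not supported:

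- **That these events can never be treatment-emergent.** Cases 2 and 4 are exceptions. The phrase about events known to precede exposure only limits a presumption for same-day and partial dates; it is not a further exclusion.
- **That they vanish from every comparison between arms.** SAE hospitalization, survival, thyroid and laboratory shifts, and dose interruption or reduction do not depend on TEAE status.
- **That the SAP removed a worsening clause that the M-SAP contained.** The M-SAP text was not available, so this cannot be known.
- **That 6.6.1 contradicts protocol 5.3.2.** That section concerns change from baseline in symptoms and is one of three listed triggers. Syncope and falls are episodic, so a new episode entered as an event has its own post-dose onset.
- **That the rule is shown to hide harm.** It applies equally to both arms. The rate difference is understated only if verdiperstat worsens such events more often than placebo does, and the documents do not quantify that.

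**Conclusion.** The gap in the stated rule is real. An AE that starts between Master Protocol consent and first dose, is kept as one record, and increases in severity or becomes serious on treatment falls outside the TEAE counts and rate differences. That includes the serious, severe, fatal and discontinuation classes. The other summaries reduce the chance that an important event goes unseen, but they do not put it back into the TEAE comparison.

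The conclusion assumes that the Master Protocol does not require worsening to be re-recorded as a new AE. The affected group is narrow: AEs arising after consent, still present at first dose, worsening on treatment, and not re-recorded. Its size cannot be computed from the documents. The case for change rests on the missing clause and the low cost of adding it, not on an estimated number of lost events.

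**What to change.** In SAP 6.6.1, define a TEAE as an AE for which any of the following falls within the stated interval: its onset, an increase in severity over the last pre-dose level, or a change to serious. State that the exception for events known to precede first exposure does not apply to an event that worsens after first dose.

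If the Master Protocol already has sites record worsening as a new AE with its own onset date, cite that rule in 6.6.1 instead; no change to the derivation is then needed.

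The cost is one sentence in the SAP and one extra flag in the AE derivation, with slightly more TEAEs in both arms. The flag needs the date on which severity or seriousness changed. The supplied documents do not show whether the AE form holds it, so this should be confirmed before data lock.
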